advised to continue ad lib (according to their own choice) diet. At the very 1st day of the study, the spirometric lung functions will be assessed by measuring forced vital capacity (FVC), forced expiratory volume in 1st second (FEV₁), forced expiratory ratio (FEV₁/FVC%), peak expiratory flow rate (PEFR) and forced mid expiratory flow of FVC (FEF_{25-75%}), maximum expiratory flow₇₅ (MEF₇₅), maximum expiratory flow₅₀ (MEF₅₀), maximum expiratory flow₂₅ (MEF₂₅) with a portable digital spirometer with a portable digital spirometer. In addition, exercise tolerance will be assessed by change in 6 minute walk distance (6MWD) in 6 minute walk test (6MWT). Changes in peripheral capillary oxygen saturation (SpO₂) by Pulse Oximeter and degree of dyspnea and fatigue by Modified Borg Scale (MBS) will also be measured both before and after 6MWT, to evaluate their changes in both the groups. All these variables will be again measured on their follow-up in 13 weeks and 26 weeks with standard pharmacological treatment of ACO with D₃ intervention (B group) and also without D₃ intervention (A group). The data will be statistically analyzed by Graphpad prism (Version 7) using independent sample 't' test (between two groups), paired Student's 't' test (between paired groups before and after intervention). Group comparisons will be done using one way ANOVA. In the interpretation of results, ≤0.05 level of probability (p) will be accepted as significant.

Expected outcome of the study:

- Impaired lung functions and exercise tolerance in vitamin D₃ deficient ACO patients will be detected and the good impact of vitamin D₃ supplementation for six months on restoration of the lung function status and exercise tolerance in ACO patients will be proved.

Key words: Asthma COPD Overlap, Vitamin D₃, FVC, FEV₁, FEV₁/FVC%, FEF_{25-75%}, PEF_R, MEF_{75%}, MEF_{50%}, MEF_{25%}, SpO₂, 6 Minute Walk Distance, Modified BORG scale.

Introduction

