Is there any improvement in lung function status and exercise tolerance in vitamin D₃ deficient ACO patients after having vitamin D₃ supplementation?

Hypothesis

Null: Vitamin D₃ supplementation does not improve lung functions and exercise tolerance in vitamin D deficient ACO patient.

Alternate: Vitamin D₃ supplementation improves lung functions and exercise tolerance in vitamin D deficient ACO patient.

Objectives:

General objectives:

To evaluate the effects of vitamin D₃ supplementation on lung function status and exercise tolerance in D₃ deficient, stable patients with ACO.

Specific objectives

- To measure the FVC, FEV₁, FEV₆, FEV₁/FVC%, PEFR and FEF_{25-75%} of vitamin D₃ deficient, stable patients with ACO, in order to assess their lung function status at baseline.
- To measure the 6MWD of all the patients, in order to assess their functional exercise capacity at baseline.
- To measure the SpO₂ at rest of all the patients, in order to assess the basal oxygenation status at baseline.
- To measure the level of dyspnea and fatigue at rest of all the patients in order to assess the basal breathlessness level at baseline.
- To measure the both the SpO₂ and level of dyspnea and fatigue again after 6MWT, for the assessment of their exercise tolerance at baseline.
- To measure the all these variables in study group at 13th weeks and at 26th weeks of their follow up.
- To measure the all these variables in control group at 13th weeks and at 26th weeks of their follow up.
- To compare all these variables in study group at baseline and endline.
- To compare all these variables in control group at baseline and endline
- To compare all these variables in both group at baseline and endline.

Methods

Type of study	: Double blinded placebo controlled trial
Place of study	: Department of Physiology, Bangabandhu Sheikh Mujib Medical University (BSMMU), Shahbagh, Dhaka
Period of study	: March 2018 to February 2019
Study population	: Stable patients of ACO with vitamin D ₃ deficiency
Sample size	: 60
Sampling	: Consecutive sampling
Grouping	:
Group A (Control)	: 30 (thirty) D ₃ deficient ACO patients with placebo administration
Group B (Study)	: 30 (thirty) D ₃ deficient ACO patients with vitamin D ₃ administration

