With these, all patients of both the groups will be advised to continue ad lib (according to their own choice) diet as well as to have sunlight exposure (within 10 am to 2 pm) only for 20 minutes daily (Manjeeta 2016).

In the mean time, a good rapport will be built up to take time to time follow-up over telephone and visiting patient's place with scheduled appointment to maintain a proper follow up at 1st (day 1) 2nd (at 13th week) and 3rd (at 26th week) visit of the study , in addition to the hematological values.

Any patient, who will be failed to follow the study procedure exactly during study period, will be dropped and a new one will be included to fulfill the desired total sample number.

Test procedure for spirometry

(Hassan 2018)

- At first, the subject will be asked to take rest sitting on a chair and remain calm and quiet for 5 minutes.
- The detailed procedure will be explained to him to ensure his maximum cooperation.
- The switch of spirometer will be on and windows will be open.
- Patients' information will be filled up and saved.
- The patient will be asked to hold a disposable paper mouthpiece (connected to spirometer) in his hand horizontally and to place it in between his two lips.
- To make good seal, he will also be asked to put the lips tightly around the outside of the mouthpiece.
- Then he will be asked to inhale first as deeply and as rapidly, as possible, which was followed by a forceful expiration for the possible longest period into the mouthpiece.
- The readings of different variables will be recorded from the spirometer monitor.
- Three (3) consecutive readings at 5 minutes interval for each parameter will be taken and the best value will be noted.

Test procedure for pulse oximetry

(Hassan 2018)

- The patient will be asked to take rest and remain calm and quiet for 10 minutes (MacAllister et al. 2007).
- The detailed procedure will be explained to him to ensure his maximum cooperation.
- Then his right index finger will be washed with alcohol and pulse oximeter sensor will be applied.
- The switch button will be on.
- The reading will be recorded from the display screen.
- Three (3) consecutive readings at 5 minutes interval will be taken and the best value will be noted.

Procedure for six minute walk test (6MWT)

(Hassan 2018)

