The 6MWT will be performed at indoors, along a long, flat, straight, enclosed corridor with a hard surface that was seldom traveled. The walking course will be 30 meter in length which was marked every 3 meter. The turnaround points will be marked with a cone. A starting line, which marked the beginning and end of each 6 meter lap, will be marked on the floor using brightly colored tape.

The subject will be asked to walk at his own maximal pace along the corridor from the end, covering as much ground as he can, during the allotted time, without running. He will be also advised to take rest if he

was too exhausted to continue the test. Standard phrases at regular intervals (every 60 seconds) will be used, like: “you are doing well,” “keep up the good work”. At the same time he will be also informed about the past time and how much left before the test completed.

If any of the subjects develop chest pain, intolerable dyspnea, leg cramps, staggering, diaphoresis or pale appearance the test will be immediately stopped and the subject will be dropped. Again, when any subject will complete the total test procedure (according to the exact protocol), he will be congratulated for good effort.

Vitamin and placebo administration

	Vitamin D₃	Placebo
Collection	Beximco Pharmaceuticals Limited, Bangladesh	Beximco Pharmaceuticals Limited, Bangladesh
Dose	80,000 IU/wk	80,000 IU/wk
Route	Oral	Oral
Ingredient	
• Cholecalciferol (40,000IU)• Microcrystalline Cellulose (58.1 gm)• Butylated Hydroxy Toluene (0.2mg)• Magnesium Stearate (3mg)• Gelatin Capsule Shell (1mg)	
• Microcrystalline Cellulose (303.8gm)• Butylated Hydroxy Toluene (0.2mg)• Magnesium Stearate (3mg)• Gelatin Capsule Shell (1mg)

STATISTICAL ANALYSIS

TITLE

**Effects of vitamin D₃ supplementation on lung functions and
exercise tolerance in D₃ deficient Asthma COPD Overlap
(ACO) patients**

Date: 06/09/2018

The results will be expressed as mean with standard error (mean \pm SE). The data will be statistically analyzed by Graphpad prism (Version 7) using independent sample 't' test (between two groups), paired Student's 't' test (between paired groups before and after intervention). Group comparisons will be done using one way ANOVA. Correlations between variables will be tested with Pearson correlation coefficient.

In the interpretation of results, ≤ 0.05 level of probability (p) will be accepted as significant.

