Past history or family history	 Previous doctor diagnosis of asthma  Family history of asthma and other allergic condition	 Previous doctor diagnosis of COPD, chronic bronchitis or Emphysema  Heavy exposure to tobacco smoke, biomass fuel
Time course	 Symptoms vary seasonally, or from year to year  May improve spontaneously or have an immediate response to BD or to ICS over weeks	 Symptoms slowly worsening over time (progressive)  Rapid acting bronchodilator provides only limited relief.
Chest X-ray	 Normal	 Severe hyperinflation

History of sun exposure:

Time : /day or week or month

Duration : /min or hour

Anthropometric data:

Height : cm Weight: kg BMI: kg/m²

Waist: cm Hip: cm Waist-hip ratio:

MUAC: cm

General examination: (present = +, absent = -)

Anaemia - / + / ++ / +++

Jaundice - / + / ++ / +++

Cyanosis - / + / ++ / +++

Clubbing - / + / ++ / +++

Edema - / + / ++ / +++

Ascites - / +

Pulse rate :

(Beats/min)

BP : Systolic:

(mmHg) Diastolic:

Systemic

examination:

Respiratory system:

Shape of the chest : Normal-1;abnormal-2

Movement of chest : Abdominothoracic-1;
thoracoabdominal-2

Tracheal position : Central-1;shifted to right-2;
shifted-3

Use of accessory respiratory muscle : Yes-1;no-2

Percussion note : Dull-1;resonant-2

Breath sound : Vesicular-1;bronchial-2

Added sound : No-1;ronchi-2;creps-3

Other system:

Heart	:	Not palpable-1;palpable-2	
Kidney	:	Not palpable-1;palpable-2	
Spleen	:	Not palpable-1;palpable-2	
Liver	:	Not palpable-1;palpable-2	

Lung function test:

Variables	MV	% of PV	MV	%	of	MV	% of PV
	Day 1	Day 1	Day 90	PV		Day 90	Day 180
	(post		(post	Day		(post	
	BD)		BD)	90		BD)	

FVC(L)

FEV1(L)

FEV1/FVC(L)

PEFR(L/S)

FEF 25-75%

(PV =Predicted Value , MV=Measured Value) \

Exercise tolerance variables

(a) 6MWD	On day	On day	On day
(meter)	0	90	180

No. of laps.....(X 60 min)+ final
partial lap.....meter

Stopped or paused before 6min (yes/no)

Reason

Symptoms at the end of exercise:

angina/dizziness/hip,leg or cuff pain

	On day 0		On day 90		On day 180	
	Before 6MWT	After 6MWT	Before 6MWT	After 6MWT	Before 6MWT	After 6MWT
(b)(SpO2)(%)						

(c) Level of
dyspnea(score)

(d) Level of

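### A patient whose 6-minute walk is stopped for symptoms is dropped at any visit, which after randomisation is exclusion tied to the exercise outcomes, with bias of unknown size and direction

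*Combined protocol and SAP*

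**What the plan says.** Exercise tolerance is an outcome named in the title. The Project Summary states that "exercise tolerance will be assessed by change in 6 minute walk distance (6MWD) in 6 minute walk test (6MWT"), with SpO₂, dyspnea and fatigue measured before and after the walk. These measurements are made at baseline and repeated at weeks 13 and 26. The Specific objectives likewise treat the post-walk SpO₂, dyspnea and fatigue readings as measures of exercise tolerance.

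The section on the six minute walk test lists chest pain and then "intolerable dyspnea, leg cramps, staggering, diaphoresis or pale appearance the test will be immediately stopped and the subject will be dropped". It does not restrict this to a walk before randomisation. The same section allows resting: "He will be also advised to take rest if he" is too exhausted to go on.

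Under Study procedure, a patient who does not follow the procedure exactly "will be dropped and a new one will be included to fulfill the desired total sample number". Whether this also covers a walk stopped for symptoms is not stated.

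The Appendix II form has, under the exercise variables, the field "Stopped or paused before 6min (yes/no"), followed by a reason, the final partial lap in metres and symptoms at the end of exercise, with columns for days 0, 90 and 180.

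The Statistical Analysis section plans the "independent sample 't' test (between two groups), paired Student's 't' test (between paired groups before and after intervention"), one-way ANOVA and Pearson correlation. It defines no analysis set, no handling of missing data and no score for a walk stopped early.

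**The concern.** Intolerable dyspnea during the walk is the severe end of an outcome the trial measures. The other triggers are signs of poor exercise tolerance or are plausibly related to it. A patient who did what was asked and was stopped by symptoms then leaves the study because of how he performed. This differs from dropping patients for non-adherence, and at weeks 13 and 26 it happens after randomisation.

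Two things are at stake. First, the arms compared at week 26 are no longer the arms that were randomised, and replacing the missing men would restore the number but not the comparison. Second, the text drops the subject, not just the test, so his spirometry and later visits are probably lost as well, and the damage may reach the lung function outcomes. Once follow-up has ended, neither the size nor the sign of the bias can be recovered.

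**Working it through.** **1. The plan's own figure.** From the Sample size calculation (the outcome variable is not named there): (1.96 + 0.84)² × (7.21² + 12.25²) / (364.1 − 357.3)² = 7.84 × 202.0466 / 46.24 = 34.257, rounded up to 35 per group. This reproduces. The root-mean-square SD is √(202.0466 / 2) = 10.05, and power at 35 per group for a difference of 6.8 is 0.81.

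**2. Model.** The documents give no stop rate, so everything below is an assumed scenario. Let follow-up 6MWD be normal with mean m and SD s, and let walks below a common distance c be stopped and dropped. With a = (c − m)/s, the share dropped is Φ(a), and the mean of those left is m + s·φ(a)/(1 − Φ(a)).

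**3. Equal spread.** Assume means 340 m (control) and 365 m (study), SD 80 m, c = 250 m.
- Control: a = −1.125, dropped 13.0%, observed mean 340 + 80 × 0.2119/0.8697 = 359.5.
- Study: a = −1.4375, dropped 7.5%, observed mean 365 + 80 × 0.1420/0.9247 = 377.3.
- Observed difference 17.8 m against a true 25 m, which is 29% too small.

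Over SD 60 to 100 m and c = 220 to 280 m, with the SD always equal in the two arms, the loss runs from 8% to 45%. At the low end, 2.3% of controls and 0.8% of the study arm are dropped.

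**4. Larger spread in the study arm.** Keep step 3 but set the study SD to 100 m. Then a = −1.15, 12.5% are dropped, and the observed mean is 365 + 100 × 0.2059/0.8749 = 388.5. The observed difference is 388.5 − 359.5 = 29.0 m against 25 m, so the benefit is overstated.

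**5. The plan's SDs.** The stated study mean lies below the control mean. To represent a benefit, the means are swapped (control 357.3, study 364.1, true difference 6.8), and c is set by the share of controls dropped.

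| Controls dropped | Equal SD 10.05 | Control 7.21, study 12.25 (as stated) | Control 12.25, study 7.21 |
|---|---|---|---|
| 2% | 6.40 (−6%) | 7.52 (+11%) | 6.19 (−9%) |
| 10% | 5.44 (−20%) | 7.69 (+13%) | 4.43 (−35%) |
| 20% | 4.64 (−32%) | 7.58 (+11%) | 2.69 (−60%) |
| 30% | 4.01 (−41%) | 7.39 (+9%) | 1.27 (−81%) |

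With equal SDs and 10% of controls dropped, power falls from 0.81 to 0.69 without replacement, or 0.72 with it.

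**6. Other stopping patterns.** If stops are unrelated to distance, a simulation gives 6.82, so the bias is about zero. If 10% of controls and 15% to 20% of the study arm are stopped, each arm losing its lowest walks (SD 10.05), the difference rises to 7.6 to 8.4.

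**7. Paired changes.** Assume SD 10.05, baseline to follow-up correlation 0.7, and the cut-off that drops 10% of controls at follow-up. A true control change of 0 is seen as +0.6, and a true study change of 6.8 as 7.0. Both within-group results are inflated. The difference between the two changes is 6.98 − 0.59 = 6.39, or 6% below 6.8. Comparing changes would therefore lose less than comparing visit values. The plan does not say which of the two the between-group test uses.

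**The case against.** A reader might infer that the rule deletes the lowest walk distances and so understates any benefit. The documents support neither part. The triggers are symptoms and signs, not a distance: a man may cramp late in a good walk, while a slow or exhausted walker may rest and stay in. The dependence on the outcome is direct only for dyspnea. The understatement needs equal spread and more stops among controls. Steps 4 to 6 show that the sign reverses when the study arm has the larger spread, as it does in the only SDs the plan gives, or when more study patients are stopped.

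The form is also not a flat contradiction of the procedure. Its field covers pauses, which are allowed, and a site could record a stop for a man who is then dropped. Nothing says that data already recorded are deleted. A stop at a baseline walk done before randomisation would be only a selection step, and the order of the two is not stated. No stop rate is given, so every magnitude is assumed and the true effect could be small.

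These points stand, and they limit what can be said about direction and size. They do not remove the problem. The rule names no visit, the walk is repeated twice after baseline, and Study procedure bases final selection on biochemical and spirometric reports without mentioning the walk. Nothing tells the analyst to keep a dropped patient.

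**Conclusion.** The concern holds as exclusion after randomisation for reasons related to the exercise outcomes, with bias of unknown size and direction. Under a pure upward shift with equal spread, a common cut-off and more controls stopped, the between-group difference in visit values moves toward no effect by 8% to 45% in the metre scenarios. With the plan's unequal SDs and swapped means, it is overstated by 9% to 13%. With stops unrelated to distance, it is about zero. Within-group paired improvements tend to be too large in the scenario examined (about +0.6 in controls with no true change, at an assumed correlation of 0.7). Stop rates, cut-offs, the means and SDs in metres, and the correlation are all assumptions. The 6MWT procedure and the Appendix II form sit uneasily together and need to be reconciled whatever the size of the bias.

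**What to change.** Leave the clinical stopping criteria as they are, and reconcile the 6MWT procedure with Appendix II so that stopping a test does not remove a randomised patient from the analysis. In the 6MWT procedure, replace the clause that drops the subject with a statement that the distance reached is recorded as that visit's 6MWD and that the existing stop, reason, partial-lap and symptom fields are completed.

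In the Statistical Analysis section, add:
- Every randomised patient's available data, including spirometry and other visits, stay in the group to which he was assigned.
- A patient whose walk is stopped is not replaced.
- The number of stopped walks, with reasons, is reported by arm and visit.
- A sensitivity analysis ranks stopped walks below all completed ones (worst rank) and compares the arms on ranks.

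Whether such a patient continues treatment or repeats the walk is a clinical decision outside this change, particularly since chest pain is one of the triggers.

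The cost is about one sentence in the procedure and a short paragraph in the analysis section. The form already has the fields. A few distances will cover less than six minutes, which the sensitivity analysis addresses.

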Therefore, on the basis of this background the present study has been designed to evaluate the effects of Vitamin D₃ on the spirometric lung function status, exercise tolerance in D₃ deficient, stable patients with ACO. This study may draw attention of the physicians about the beneficial effects of the vitamin D₃ on both pulmonary and extrapulmonary manifestation in ACO patients.

Rationale

In recent years, ACO has gained much attention and have extensively reviewed worldwide. There is a scarcity of population-based data on ACO in Bangladesh except Habib et al. As patients with ACO seem to be at risk for a poor outcome, high risk of exacerbations, it is of utmost importance to perform more research on this significant disease.

However, as far as it has been searched association of vitamin D status with ACO has only seen by Odler et al. (2015) who reported significant decrement of serum 25(OH)D in elderly ACO patients. Strikingly no study have been conducted to observe the effects of this fat soluble vitamin on lung function and exercise capacity in vitamin D₃ deficient, stable patients with ACO.

To the best of our knowledge, as far as we reviewed with a loading dose followed by upto 50,000 IU/week of oral D₃ for 12 weeks, could not improve the spirometric variables in stable COPD patients (Said and Elnaeem 2014; Hornikx et al. 2015; Moosavi and Shoushtari 2015; Rezk et al. 2015). Whereas, Nazarian et al. (2011) found significant improvement of insulin sensitivity in patients with Type II Diabetes meliitus after 4 weeks oral supplementation of 10,000IU/day vitamin D₃ (Nazarian et al. 2011). On the basis of this observation, we have selected 80,000 IU/ week of oral vitamin D₃ , for consecutive 13 weeks followed by 40,000 IU / 1 to 6 week for further consecutive 13 weeks, as the dosage schedule for our D₃ deficient patients of stable ACO. In addition,

as toxicity dose of vitamin D₃ is very high (50,000IU/day for several months) (Veith 1999), this dose schedule will be safe for our patients.

Therefore, on the basis of this background the present study has been designed to evaluate the effects of Vitamin D₃ on the spirometric lung function status, exercise tolerance in D₃ deficient, stable patients with ACO. This study may draw attention of the physicians about the beneficial effects of the vitamin D₃ on both pulmonary and extrapulmonary manifestation in ACO patients.

Research question

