If the patient with D₃ deficiency [Serum 25(OH)D <30 ng/ml] and not with renal insufficiency (Serum creatinine >1.3 mg/dl), then the Fasting blood sugar, serum HbA_{1c}, serum parathormone (PTH), serum calcium (Ca²⁺), serum phosphate (PO₄³⁻), serum alkaline phosphatase (ALP), serum SGPT, serum cholesterol, serum High Density Lipoprotein (HDL), serum low density lipoprotein (LDL), serum triglyceride (TG), will be assessed from the preserved blood.

After that their height and weight will be measured and the spirometric lung function test will be done by using a portable spirometer (PONY FX, cosmed, Italy]. After getting all the biochemical and spirometric reports the final selection will be done, according to the inclusion and exclusion criteria. All the eligible patients will be randomly assigned to either 'Control' or 'Study' groups and will be thoroughly informed about the objectives and detailed study procedure, once again.

Subsequently a standard therapeutic treatment (according to GOLD guideline) will be prescribed to all the selected stable ACO patients of both groups. Proper education will be given about drug, method of taking medication and medication plan.

Along with the standard pharmacological treatment of ACO, the patients of the 'Study group' will be prescribed for 80,000 IU/ week of oral vitamin D₃, for consecutive 13 weeks. Subsequently, all the patients will be cordially requested to again visit the Department of physiology, BSMMU, on 13th week of their follow up to reexamine all the study

variables along with serum 25(OH)D and Ca^{2+} (to check the toxicity). These data will be recorded as values of '13th week' (B13).

Then according to serum level of 25(OH)D and Ca^{2+} (American Vitamin D council 2017), 40,000 IU / 1 to 6 week oral vitamin D₃ will be prescribed, for further 13 weeks. At 26th week of follow up, they will be requested again to visit the Department of Physiology, BSMMU, to reexamine all the study variables, and the data will be recorded as values of '26th week' (B26).

Similarly, all the patients of 'control group' will be prescribed for placebo (along with standard pharmacological treatment of ACO, prescribed by pulmonologist) for consecutive 26 weeks and their respective data will be recorded as A13 and A26.

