Appendix IV

Cholecalciferol supplementation schedule for D₃ deficient [serum 25(OH)D<30 ng/ml] ACO pts

Our aim is

- to avail (within 6 months) and maintain serum 25(OH)D @ 60-80 ng/ml + serum Ca²⁺ @ 8.5-10.5 mg/ml,
- for having extra-calcaemic effect of vitamin D₃,
- on lungs and other tissues

At 1st visit / at day 0:

Cholecalciferol 80,000 IU (2 capsules of 40,000 IU) / wk, for 12 weeks (3 months)

At 2nd visit / at day 90 / after 3 months:

If, serum 25 (OH)D + serum Ca ²⁺ =	Then, for next 3 months, prescribed dose will be -	So, for next 3 months, dose schedule will be -
30-40 ng/ml + 8.5-10.5 mg/ml	4600 IU/day	4600 IU X 7 = 32,200 IU / 7 days = 1 cap (40,000 IU) / wk
40-50 ng/ml + 8.5-10.5 mg/ml	3000 IU/day	3000 X 15 = 45,000 IU / 15 days = 1 cap (40,000 IU) / 2 wks
60-80 ng/ml + 8.5-10.5 mg/ml	not suggested in guideline, but, to get extra-calcaemic effect of D₃	1 cap (40,000 IU) / 6 wks
> 80 ng/ml + 8.5-10.5 mg/ml	stop taking drug & symptom analysis	no dose for 3 months
>150 ng/ml + >10.5 mg/ml	close monitoring and ask for – 
 • feeling sick or being sick • poor appetite or loss of appetite • feeling very thirsty • passing urine often 	no dose for 3 months

	
• constipation or diarrhea• abdominal pain• muscle weakness• pain• bone pain• feeling confused• feeling tired	
--	---	--

At 3rd visit / at day 180 / after 6 months:

Pt will be referred to physician and will be suggested to follow the above-mentioned schedule

Ref: Vitamin D Council. I tested my vitamin D level. What do my results mean? 2017 [Internet]. [Cited 2018 March 25]. Available from: <https://www.vitamindcouncil.org/i-tested-my-vitamin-d-level-what-do-my-results-mean/>

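### Calcium and 25(OH)D are re-measured as a toxicity check, but the analysis plan never counts or lists patients above a limit by arm

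*Combined protocol and SAP*

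**What the plan says.** The Project Summary and the Study procedure section both bring patients back at week 13 to re-examine "variables along with serum 25(OH)D and Ca^{2+} (to check the toxicity". At week 26 all study variables are measured again. The data schedule in Appendix II has day-90 and day-180 columns for both laboratory values.

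The inclusion criteria admit only patients with calcium of 8.5–10.5 mg/dl. Appendix IV sorts each patient at day 90 by his own 25(OH)D and calcium. It has separate rows for 25(OH)D above 80 ng/ml with calcium in range, and for 25(OH)D above 150 ng/ml together with calcium above 10.5. The second of these calls for "close monitoring and ask for" a list of symptoms.

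The Statistical Analysis section is a few lines long. On summaries it says "The results will be expressed as mean with standard error (mean \pm SE". For testing it names t-tests, independent-sample for the two arms and paired for change within an arm, and a one-way ANOVA. For association it names Pearson's coefficient. The significance threshold is 0.05. The Rationale says in advance that "this dose schedule will be safe for our patients".

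**The concern.** Toxicity from supplementation is a property of individual patients at the upper end of the distribution, and Appendix IV treats it that way. The analysis section does not. Each listed method reduces the arm to a mean, a difference in means or a linear correlation. None answers the safety question: how many patients in each arm went above the limit, and how far.

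Because every patient enters with calcium at or below 10.5 mg/dl, any later value above it is new since baseline and belongs in the report. If the plan is followed as written, a reader would see two mean calcium values with standard errors. Those values could look normal with no affected patients or with several. The p-value does not separate these cases reliably, because it depends mainly on what happens to the unaffected majority.

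**Working it through.** **Group size.** The sample-size section gives (1.96 + 0.84)² × (7.21² + 12.25²) / 6.8² = 7.84 × 202.0466 / 46.24 = 34.26, rounded up to 35 per group. This reproduces. The Methods list gives 30 per group, so both sizes are used where it matters.

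**Assumptions.** The documents give no calcium mean or SD. Assumed: mean 9.5 mg/dl (midpoint of the eligibility range), SD 0.3–0.5, affected patients at 11.5 mg/dl.

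**Arm mean with 3 of 35 affected, no change in the other 32.** (32 × 9.5 + 3 × 11.5) / 35 = 338.5 / 35 = 9.67 mg/dl, which is 0.83 below the limit.

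**Share of the arm needed to take the mean past 10.5.** If the rest stay at 9.5, the share is (10.5 − 9.5) / (high value − 9.5): 40% at 12.0, 50% at 11.5 and 67% at 11.0.

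**Planned between-group t-test, two-sided 0.05, at least 20,000 simulated trials per setting, 35 per arm, no shift in the rest:**

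| Patients at 11.5 | Significant trials, SD 0.3–0.5 |
|---|---|
| 1 | about 5% |
| 2 | 8–9% |
| 3 | 14–19% |
| 4 | 23–34% |
| 5 | 35–55% |

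With a baseline mean of 9.2 or 9.5, high values of 11.0 or 12.0, and 30 or 35 per arm, three affected patients give 12–20%.

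**Same setting, three affected, but the other 32 also rise by 0.2 mg/dl.** The mean is (32 × 9.7 + 3 × 11.5) / 35 = 344.9 / 35 = 9.85 mg/dl, still inside the range. The t-test is now significant in about 70% of trials at SD 0.5, 85% at SD 0.4 and 96–97% at SD 0.3. That significance comes largely from the 0.2 shift and does not show that three patients passed 10.5.

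**What a count would show (exact 95% limits).**

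| Patients above limit | n = 35 | n = 30 |
|---|---|---|
| 0 | 0–10.0% | 0–11.6% |
| 1 | 2.9% (0.1–14.9%) | 3.3% (0.1–17.2%) |
| 3 | 8.6% (1.8–23.1%) | 10.0% (2.1–26.5%) |

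The zero-event limit is 1 − 0.025^(1/n). At a true risk of 5%, the chance of at least one affected patient is 1 − 0.95^35 = 83% (79% with 30), so a count would usually show something.

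**A significance test on the counts would not help.** Fisher's exact test gives p = 0.24 for 3 versus 0 and p = 0.05 for 5 versus 0 (0.054 with 35 per arm, 0.052 with 30). Counts, limits and highest values are what is needed.

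**The case against.** The strongest reply is that the toxicity check is already made patient by patient. The week-13 values lead directly into the Appendix IV schedule, so many high values would be seen by the people treating the patient. This stands. A reader might infer that hypercalcaemia would go undetected, and the documents do not support that. What is missing is the step from individual review to tabulation and reporting by arm.

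A reader might also infer that the trial is set to report a safe result with a non-significant p-value. That goes too far as well. The specific objectives contain no safety objective, and nothing says safety will be judged on mean calcium. The Rationale's statement is an advance justification of the schedule, not a planned conclusion. The p-value could fall either way, as the 0.2 mg/dl shift shows.

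Three limits on the point also stand:

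- Only week 13 is labelled a toxicity check. Week 26 follows from the re-examination of all study variables and from the data schedule.
- Appendix IV pairs calcium above 10.5 only with 25(OH)D above 150 ng/ml. A stand-alone calcium count takes its limit from the inclusion range, not from an Appendix IV rule.
- A short part of the document directly after the statistics section was not available, so the absence of a count can be stated only for the text that was.

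**Conclusion.** The gap is real and should be closed, but it is a gap in analysis and reporting, not in patient-level review. Followed as written, the plan would not show how many patients in either arm exceeded a calcium or 25(OH)D limit.

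The result that does not depend on the p-value is that the arm mean stays inside 8.5–10.5 mg/dl with several patients above it (9.67 or 9.85 mg/dl with three of 35). The 14–19% figure is conditional: it rests on the assumed mean, SD and high value, and on no shift in the other patients. With a 0.2 mg/dl shift it becomes about 70–97%. Neither figure should be quoted without its condition. The efficacy analyses are unaffected.

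**What to change.** Add to Statistical Analysis: for each arm, at week 13 and at week 26, report the number and percentage of patients with serum calcium above 10.5 mg/dl (upper limit of the inclusion range), 25(OH)D above 80 ng/ml, and 25(OH)D above 150 ng/ml (Appendix IV), with exact 95% confidence intervals and the highest individual value.

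The denominator should be patients with a value at that visit. It should include anyone measured before being dropped or replaced under the Study procedure rule. State per arm how many were dosed but not measured. A denominator of all dosed patients would count the unmeasured as normal and lower the rate.

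State that any safety conclusion rests on these counts and upper limits, not on mean calcium.

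Before the limits are applied, reconcile the units. Calcium is in mg/ml in Appendix IV and mg/dl in the inclusion criteria and data schedule. 25(OH)D is in mg/ml in the data schedule and ng/ml elsewhere. No dose or clinical rule is proposed here.

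The cost is a few sentences and one table, from values already on the form. The safety statement also becomes less favourable, since with no events a rate of up to 10.0% (35 per arm) or 11.6% (30 per arm) is not excluded.
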